6.2.9 Multiple timepoints

Visits following the Week 2 (and possible Week 4) site visit(s) and the Week 6 TC will be binned based on time elapsed since the baseline visit; visits falling into the same interval of time will be given the same label for reporting. The binning will be done on a monthly level, with visit days rounded to the nearest full month, using a conversion factor of 1 month = 30.4375 days.

6.2.10 Checking model assumptions

Not applicable.

6.2.11 Transformations

No data transformations are planned.

6.2.12 Multicentre studies

Subject disposition will be tabulated by centre. No additional reporting by centre will be done.

6.2.13 Interim analyses and data monitoring

None planned.

6.2.14 Subgroups

Summary of AEs and AESIs will be presented in the subgroups of: age; sex; race; BMI; acetylation status; and baseline medical history groups of interest (see 7.3).

6.2.15 Descriptive statistics

The following statistics will be provided for continuous variables: number of observations, mean, standard deviation (SD), minimum, median and maximum. For categorical variables, frequency counts and percentages will be presented.

Mean, median and SD values will be presented to one more decimal place than the raw values. Minima and maxima will be presented as they appear. Percentages will be rounded to the nearest single decimal place, with the exception of 0 and 100, which will be presented as integers.

When descriptive statistics are reported by treatment group, data for a pooled total arm will also be reported, unless otherwise specified.

7. STATISTICAL ANALYSES

The subject's assigned arm from REFALS will be used when reporting by treatment group.

7.1 Disposition of subjects

329 subjects completed the REFALS study. Of those, 28 were ineligible to continue to the extension study, and 54 otherwise eligible subjects did not wish to continue. Of the remaining 247 subjects who wished to continue, 20 were delayed due to COVID-19 related restrictions, and did not start the study before the recruitment was closed. In total, 227 subjects were screened and started the extension.

The number of subjects will be tabulated by treatment group for the following populations:

- Screened population
- Safety population
- Discontinued study

Separate tables by treatment group will also be provided for each country, and each study centre.

The disposition and number of subjects, along with reasons for screening failure and study discontinuations, will be listed and tabulated by treatment group.

7.2 Demographic and other baseline characteristics

Descriptive statistics (see 6.2.15) of demographic and other baseline characteristics will be tabulated for the safety population, stratified by treatment group. An authorised person will code medical history and concomitant diseases using standard coding dictionaries (see 7.10.1).

The following variables will be summarized:

1. Age
2. Age (< 65, 65–74, ≥ 75)
3. Sex
4. Race
5. Ethnicity
6. Height
7. Weight
8. BMI
9. BMI (< 18.5, 18.5–24.9, 25.0–29.9, ≥ 30.0)
10. Country
11. Region (North America, rest of the world)
12. Site of onset (bulbar, spinal)
13. El Escorial criteria for ALS diagnosis
14. Disease duration (time from symptom onset to baseline)
15. Below median disease duration (time from symptom onset to baseline)
16. Time from symptom onset to baseline (observed tertiles)
17. Time from symptom onset to baseline (observed quartiles)
18. Acetylation status (slow, rapid; see 7.7)
19. Acetylation status (4 groups; see 7.7)
20. Cardiac or vascular abnormality (see 7.3)
21. Ischaemic heart disease (see 7.3)
22. Cardiac arrhythmias (see 7.3)
23. Cardiac failure (see 7.3)
24. SVC (sitting) at baseline
25. Below median SVC (sitting) at baseline
26. SVC (supine) at baseline
27. Below median SVC (supine) at baseline
28. King's clinical stage at baseline (see 7.5.2.1)
29. ALSFRS-R at baseline
30. Below median ALSFRS-R at baseline
31. ALSFRS-R bulbar subdomain at baseline
32. ALSFRS-R fine motor subdomain at baseline
33. ALSFRS-R gross motor subdomain at baseline
34. ALSFRS-R respiratory subdomain at baseline
35. ALS progression rate at baseline
36. ALS progression rate at baseline (< 1 point/month, ≥ 1 point/month)
37. ALS progression rate at baseline (observed tertiles)

Values for the above variables will be summarized also at REFALS baseline as part of the additional combined reporting described in 7.10.4.

7.3 Medical history

Medical history will be coded with the Medical Dictionary for Regulatory Activities (MedDRA) version 23.1. Descriptive statistics will be provided by body system organ class (SOC), and preferred term (PT), by treatment group.

Past findings, where the subject reports the condition has ended prior to their start of the study, and present findings, those ongoing at the start of the study, will be reported separately.

The following categories define groups of interest used in safety subgroup analyses:

1. Cardiac or vascular abnormality
2. Ischaemic heart disease (SMQ)
3. Cardiac arrhythmias (SMQ)
4. Cardiac failure (SMQ)

Both past and present findings at the start of the study are included in forming these groups. See Appendix 10.1 for definitions of the search categories. If an SMQ has both a broad and a narrow definition, the narrow search will be used.

7.4 Extent of exposure and treatment compliance

The total number of exposed subjects, the total duration of study treatment exposure (continuous, and categorized both separately and cumulatively at the thresholds of ≤ 4 , ≤ 8 , ≤ 12 , ≤ 24 , and ≤ 48 weeks), and dose levels (in milligrams), averaged over the course of the study as well as at each study visit, will be reported as measures of extent of exposure.

Dose changes will be described by reporting the subject counts in the following categories:

- 1) remained at 1 mg for the entire study (“never increased”)
- 2) uptitrated to 2 mg and remained for the rest of the study (“increased and remained”)
- 3) uptitrated to 2 mg and later downtitrated to 1 mg (“increased, then decreased”)
- 4) downtitrated to 0.5 mg directly (“decreased directly”).

Treatment compliance will be described by reporting the number of dispensed and returned study treatment capsules at each study visit. The number of subjects with treatment interruptions longer than 7 days will be reported with descriptive statistics.

Both extent of exposure and treatment compliance will be tabulated with descriptive statistics.

7.5 Efficacy

All efficacy data will be listed and tabulated by treatment group for each visit.

7.5.1 Primary efficacy variable(s)

7.5.1.1 Slow Vital Capacity

SVC is defined as the maximum volume of air that the subject can exhale slowly after slow maximum inhalation. The raw SVC volume is measured in litres. The SVC variable used in the

analyses is derived from the raw SVC volume, and measured as a percentage of the predicted (normal) volume for age, height and sex. Predicted values used for the calculation are derived based on the global lung function 2012 equations (Quanjer PH et al., 2012).

SVC will be assessed in the sitting and supine position once at each centre visit during the study including the baseline (visit 1), i.e. in the morning before the study treatment administration. The MasterScope (used in the REFALS study) with centralised reading will be used in all study centre visits during the first 3 months (so that all subjects have at least 1 post-baseline assessment with the device), after which each centre will either use its own standard pulmonary function test equipment or continue using the MasterScope without centralised reading. At baseline (visit 1), the SVC will be assessed by using both MasterScope and the local equipment.

Descriptive statistics will be reported by treatment group for SVC in both supine and sitting positions (including original values, and change from baseline) at each study visit. For supine SVC, descriptive statistics will also be further broken down by angle of measurement.

Slope of decline will be estimated for both treatment groups, using a random slope model for change from baseline. To facilitate comparison with the main study, the model will be adjusted for REFALS randomization strata, and include the baseline measurement as a covariate.

Measurements made with local devices (or MasterScope without centralised reading) and MasterScope devices with centralised reading will be reported separately, along with a third combined measurement which includes measurements from either type of device, preferring the MasterScope measurement with centralised reading if both are present on a given visit. Measurements of unacceptable quality (BTRGRCD = "U") will be excluded from reporting.

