
Investigational product, dose and mode of administration: Test product will be Levosimendan 1 mg capsules administered orally. The target maintenance dose of oral levosimendan will be 2 mg/day taken as 1 mg b.i.d.

Levosimendan treatment will be started at 1 mg/day, with increase to 2 mg/day after 2 weeks treatment if well tolerated.

Frequency/duration of treatment: The subject may continue the treatment as long as clinically indicated or until the study ends.

Variables and methods of assessments:
 
Efficacy assessments:
 
Slow vital capacity (SVC): SVC will be assessed in the sitting and supine position once at each centre visit during the study including the baseline, i.e. in the morning before the study treatment administration.
 
Revised ALS Functional Rating Scale (ALSFRS-R): ALSFRS-R will be assessed at each centre visit and telephone contact. The variables derived will be the scores of the 12 separate items, the total scores of each subdomain (bulbar, fine motor, gross motor and respiratory) and the total score of ALSFRS-R.
 
Need for respiratory support: The use of any respiratory support, including Bilevel Positive Airway Pressure (BiPAP) and invasive mechanical ventilation, will be recorded. The time to starting or changing the degree of respiratory support will be calculated.
 
Borg Category Ratio 10 Scale (CR 10): Borg CR 10 scale will be used in the assessment of dyspnoea. The subjects will be asked to point out a score quantifying their perception on the intensity of dyspnoea on the CR10 scale at rest in sitting and supine position (immediately before the SVC measurements). Orthostatic changes between sitting and supine positions will be calculated.
 
Health care and home care resource use: Health care and home care resource use will be recorded for possible later use in pharmaco-economic analysis.
 
Other assessments: Subject's status for tracheostomy and survival will be recorded at all visits.
 
Safety assessments
 
Safety will be assessed by adverse events (AEs), vital signs, 12-lead electrocardiogram (ECG) and by assessment of suicidality.

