1.2 Rationale of the study

1.2.1 Rationale of the study design

This study provides an opportunity for subjects in the REFALS study to continue treatment with oral levosimendan. The study will also provide more information about long-term safety and effectiveness of oral levosimendan in patients with ALS, to supplement data from the double-blind REFALS study.

This is an open-label study, so that all eligible subjects that complete the double-blind REFALS study will have the opportunity to receive oral levosimendan treatment. Apart from completing the REFALS study, eligibility criteria for REFALS-ES study are restricted to safety criteria that may have changed since the start of the REFALS study. The subjects will be able to participate in the study and receive levosimendan for as long as it is considered clinically beneficial. In addition, as a long term extension, the objective is to limit disruption to usual patient care and to reduce subject inconvenience and study commitments. Thus safety and efficacy measures and study restrictions are reduced to more closely reflect typical patient care than in the double-blind study. On completing 48 weeks double-blind treatment in the REFALS study, all subjects will stop blinded treatment, with the REFALS end-of-study visit 14-25 days later serving as the baseline visit for REFALS-ES study and re-initiation of the treatment. Since the half-life of the most important active metabolite of levosimendan, OR-1896, exceeds 60 hours, the actual drug-free period will be somewhat shorter than this. This off-treatment period allows evaluation of reversal of ongoing AEs as well as observation of the effects of withdrawal of prolonged levosimendan treatment. It also reduces any risk of unblinding occurring as a result of an abrupt change in the treatment for subjects receiving placebo in REFALS study. As levosimendan is intended for treatment of respiratory symptoms rather than preventing or delaying disease progression, the break in treatment is not expected to result in a significant risk to subject well-being.

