2.2 Secondary objective

The secondary objective is to explore long-term effectiveness of oral levosimendan in the treatment of patients with ALS, by continuing to observe rate of disease progression during the treatment.

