6.1.4 Procedures during the post-treatment period

An end-of-study visit will take place 14-25 days after the last study treatment administration for each subject. The following procedures will be performed:

- Pulse/heart rate and BP will be recorded.
- SVC supine and sitting will be assessed.
- A pregnancy test will be performed for females of childbearing potential.
- AEs, current medical conditions and concomitant treatments will be recorded.
- Status for NIV support, invasive mechanical ventilation by intubation or tracheostomy and survival will be recorded
- Suicidality will be assessed.

In case it is not possible for the subjects to travel to the study centre, the end-of-study visit may be performed by telephone (except pregnancy test, BP and SVC).

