7.5.2 Secondary efficacy variables

7.5.2.1 Revised ALS Functional Rating Scale

The ALSFRS-R (Cedarbaum JM et al., 1999) includes 12 items: speech, salivation, swallowing, handwriting, cutting food and handling utensils, dressing and hygiene, turning in bed and adjusting sheets, walking, climbing stairs, dyspnea, orthopnea, and respiratory insufficiency. Each item will be scored from 0 to 4, with lower values indicating worse function. The variables derived will be the scores of the 12 separate items, the total scores of each subdomain (bulbar [items 1-3], fine motor [4-6], gross motor [7-9] and respiratory [10-12]) and the total score of ALSFRS-R.

Descriptive statistics will be reported by treatment group for all items in the scale, as well as each subdomain and the total scale at each study visit (original values, and change from baseline).

Slope of decline will be estimated for both treatment groups, using a random slope model for change from baseline. To facilitate comparison with the main study, the model will be adjusted for REFALS randomization strata, and include the baseline measurement as a covariate.

Further, time to decline from baseline in an ALSFRS-R respiratory domain score (items 10–12) will be described (see [7.5.2.2](#)).

To describe the study population, two additional variables will be derived from the ALSFRS-R:

King's clinical stage is a staging system used to measure the clinical progression of the ALS disease across body system regions. Staging is not directly collected as part of the study. Instead, King's clinical stage will be estimated from the ALSFRS-R as follows (Balendra, 2014):

1. Respiratory failure (Item 10 = 0 or Item 12 < 4) ⇒ Stage 4b
2. Nutritional failure (answered item 5b) ⇒ Stage 4a
3. For lower stages, count the number of regions involved:
 - a. Bulbar (any of items 1–3 < 4)
 - b. Upper limbs (either of items 4 and 5a < 4)
 - c. Lower limbs (item 8 < 4)

King's stage is used to describe disease progression status at baseline.

ALS progression rate at baseline will be calculated as the number of points missing from a full ALSFRS-R score (48) at baseline divided by the time (in months) between symptom onset and the baseline ALSFRS-R measurement.

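### The SVC and ALSFRS-R slope models have no on/off-treatment rule, so end-of-study records taken 14-25 days off drug can enter a slope meant to describe progression during treatment

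*SAP*

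**What the plan says.** The secondary objective (Protocol 2.2, repeated in SAP 3.2) is to explore effectiveness "by continuing to observe rate of disease progression during the treatment".

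SAP 7.5.1.1 (SVC) says: "Slope of decline will be estimated for both treatment groups, using a random slope model for change from baseline". SAP 7.5.2.1 (ALSFRS-R) repeats this, and in both sections "the model will be adjusted for REFALS randomization strata, and include the baseline measurement as a covariate". The only stated exclusion is SVC of unacceptable quality. SAP 6.2.9 labels later visits by time alone: they "will be binned based on time elapsed since the baseline visit". SAP 6.2.4 treats intercurrent events as not applicable, and SAP 7.5.4 plans no sensitivity analysis.

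Protocol 6.1.4 says: "An end-of-study visit will take place 14-25 days after the last study treatment administration for each subject". At that visit "SVC supine and sitting will be assessed", and Table 1 assigns this to local equipment. Table 1 also marks ALSFRS-R at end of study, and the synopsis says "ALSFRS-R will be assessed at each centre visit and telephone contact", but the list in Protocol 6.1.4 omits it.

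The SAP does address stopping treatment elsewhere: the time-to-event censoring table (SAP Table 1) has a row for it. The slope sections have nothing comparable.

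**The concern.** The protocol's own pharmacology makes the off-drug record a different kind of observation. Protocol 1.2.1 reasons: "As levosimendan is intended for treatment of respiratory symptoms rather than preventing or delaying disease progression", and says that the 14-25 day gap at the end of REFALS allows withdrawal effects to be observed. The gap after the extension has the same length. Protocol 1.1 reports that supine SVC improved after 14 days of treatment in the phase II study.

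If such an effect exists, on-treatment values sit above the underlying trajectory and the end-of-study value does not. That value is also the last in time and has high leverage on the slope. A model with time as its only within-subject term would absorb the step as part of the rate of decline.

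Two outputs are most exposed: the absolute slope in each group, and the time-by-study-by-arm interaction in SAP 7.10.4. The interaction looks for a change in slope when placebo subjects move to active drug. Those subjects have a withdrawal from levosimendan only in the extension.

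**Working it through.** The plan gives no figure to reproduce: it has no hypothesis, sample-size calculation or assumed effect.

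**Is the end-of-study visit off drug?** Protocol 1.2.1 puts the half-life of the active metabolite above 60 hours. At day 14, 14 × 24 / 60 = 5.6 half-lives have passed, and 0.5^5.6 = 0.021, so about 2% remains. At an assumed 80 hours it is about 5%.

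**Assumptions.** Centre visits at week 2 and every 3 months; last dose at the last on-drug visit, month F; end-of-study visit 20 days later; 1 month = 30.4375 days (SAP 6.2.9). Week 2 is then 0.460 month and end of study is t_E = F + 0.657. On-drug visits carry a constant gain of d points and the end-of-study visit carries none. Baseline is off drug, so this pattern carries over to change from baseline.

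**Formula.** With a free intercept and post-baseline rows only, the slope bias is

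−d × (t_E − mean t) / Σ(t − mean t)².

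For subjects on one common schedule, a random intercept-and-slope model gives the same value as least squares.

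For d = 1:

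| Last on-drug visit | t_E − mean t | Σ(t − mean t)² | Bias (points/month) |
|---|---|---|---|
| Month 3 | 1.285 | 5.702 | −0.225 |
| Month 6 | 2.628 | 24.589 | −0.107 |
| Month 9 | 4.034 | 61.357 | −0.066 |
| Month 12 | 5.471 | 120.567 | −0.045 |

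The values scale with d. A gap of 14 or 25 days instead of 20 changes the month 3 value only to −0.221 or −0.227. Adding the week 6 call, as for ALSFRS-R, gives −0.24, −0.11, −0.06 and −0.04.

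**Local-device series.** Its on-drug readings start after month 3. With visits at 6, 9 and 12 months, the same formula gives −0.19 for exit at month 9 and −0.10 at month 12. Exit at month 6 leaves two points 0.657 month apart and says little about slope.

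**Pooled check.** A mixed model was simulated with 227 subjects, 25 replicates and equal shares of the four follow-up lengths. Assumed values were a true slope of −2.0, residual SD 5, intercept SD 3 and slope SD 1.5. Strata and the baseline covariate were left out.

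| d | End of study included | End of study excluded | Off-treatment term |
|---|---|---|---|
| 0 | −2.01 | −1.99 | −1.99 |
| 2 | −2.17 | −1.99 | −2.00 |
| 4 | −2.34 | −1.97 | −1.97 |

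Monte Carlo standard errors are 0.02 to 0.03.

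**Dependence on baseline handling.** Suppose the off-drug baseline is instead an outcome row with change zero at time 0. For d = 1:

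| Last on-drug visit | End of study kept | End of study dropped | Off-treatment term on baseline and end of study |
|---|---|---|---|
| Month 3 | −0.010 | +0.221 | 0 |
| Month 6 | −0.006 | +0.104 | 0 |
| Month 9 | −0.003 | +0.064 | 0 |
| Month 12 | −0.002 | +0.044 | 0 |

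Under this coding a term on the end-of-study visit alone gives the same result as dropping that visit.

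**The case against.** The strongest objection is that the direction depends on a choice the SAP does not state. A reader might infer that the plan necessarily overstates decline and that dropping the end-of-study visit cures it. The documents do not support that. With baseline as a zero-change row the bias nearly cancels, and dropping the visit then makes the decline look slower. If the line is forced through zero, the bias is positive with or without the visit. This part stands, and the fix must cover it. The free-intercept reading is still the usual one for a change score with baseline as covariate.

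Other limits also stand:

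- **Outcomes.** A reader might apply the argument equally to supine SVC, sitting SVC and ALSFRS-R. Protocol 1.1 reports improvement in supine but not sitting SVC, and no acute effect on ALSFRS-R is reported.
- **Device.** A reader might infer a device change at the end-of-study visit. The move away from centrally read MasterScope comes after month 3, so a coincident change arises only for exits by about 3 months, in the combined series. The centrally read series should hold no end-of-study value.
- **Inclusion is inferred.** It rests on the absence of an exclusion, and SAP 6.2.9 concerns reporting labels. Some end-of-study visits will lack SVC because they were by telephone or under COVID-19 arrangements.
- **Size.** No effect size or follow-up distribution is given. Early termination (SAP 7.11) suggests shorter follow-up but does not quantify it.
- **Consequence.** Both groups take levosimendan, so the arm contrast within the extension is largely protected if follow-up is similar. No hypotheses are tested, reporting has been narrowed, and the combined analyses lie outside the study report.

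None of this supplies the missing rule. The slope models remain planned outputs for the secondary objective.

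**Conclusion.** The gap is real and worth closing: the slope sections do not separate on-treatment from off-treatment records. Under a free intercept with post-baseline changes only, each point of lost acute effect biases the slope by about −0.23 to −0.05 points/month as the last on-drug visit moves from month 3 to month 12. In the simulated mix of follow-up lengths the shift from the d = 0 run was −0.16 for a 2-point effect (−2.17 against −2.01) and −0.33 for a 4-point effect (−2.34 against −2.01).

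These figures rest on an assumed effect size and visit pattern, and the bias is zero if there is no acute effect. The case is best supported for supine SVC in the local-device and combined series, in the absolute slopes and the SAP 7.10.4 interaction. The documents do not show that the planned slopes are in fact biased, or that the comparison between former arms within the extension is compromised.

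**What to change.** In SAP 7.5.1.1 and 7.5.2.1, and by the same rule in 7.10.4, state that:

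1. the slope model has a free intercept;
2. the off-drug baseline enters only as a covariate, not as a zero-change outcome row;
3. records after the last dose are flagged off-treatment and either left out of the slope or kept with an off-treatment term.

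If baseline is kept as an outcome row, the off-treatment term must cover baseline as well as end of study. Report the change from the last on-drug visit to end of study separately, as an off-treatment result. Reconcile Protocol Table 1 with Protocol 6.1.4 on whether ALSFRS-R is assessed at end of study.

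The cost is a few sentences and one flag derived from the last-dose date. Leaving the records out loses one slope point per subject and slightly lowers precision. Subjects left with a single on-drug reading in a series then add little to its slope.
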